9.1.1. Primary Efficacy Assessment

The primary endpoint is the response on the NPI-Psychosis subscale items of delusions and hallucinations and/or the agitation/aggression domain.

9.1.2. Secondary Efficacy Assessment

Following secondary endpoints were removed: Clinical Global Impression of Severity; Cohen Mansfield Agitation Inventory (CMAI); Alzheimer's Disease Cooperative Study-Activities of Daily Living Inventory (ADCS-ADL).

The following endpoint was added:

Clinical Global Impression of Improvement (CGI-I; Guy et al. 1976)

The CGI-I is a 7-point scale that requires the clinician to assess how much the patient's illness has improved or worsened relative to baseline (Visit 2). The scale ranges from 1 (very much improved) to 7 (very much worse).

9.3. Exploratory Efficacy Assessment

Following exploratory endpoint was removed: Alzheimer's Disease Cooperative Study-Clinical Global Impression of Change (ADCS-CGIC).

The following endpoint was added:

Zarit Burden Interview-22 (ZBI-22; Zarit et al. 1980)

Changes in caregiver burden will be assessed using the Zarit Burden Interview-22 (ZBI-22). The ZBI-22 is a 22-point scale used to assess caregiver burden in the dementia patient population (Zari et al. 1980). Each of the 22 items is rated on a scale of 0 to 4, where 0 = never, 1 = rarely, 2 = sometimes, 3 = frequently, 4 = nearly always. The total score of the ZBI-22 is the sum of those 22 items.

9.5.1 Pharmacokinetic Sampling

PK sample collection scheduled at Week 8 (Visit 7) was moved to Week 10, Visit 8 (2 to 4 hours postdose).

Section 10. Statistical Considerations and Data Analysis

10.1. Sample Size Determination

Approximately 200100 patients will be enrolled to enable approximately 16080 evaluable patients to complete the study through at least Visit 5 (Week 4). The sample size was chosen so that there is at least a 76 80% chance the trial will show a 65% or greater Bayesian posterior probability of at least a 1 point improvementstatistically significant improvement in the response rate on the NPI-Psychosis scale (hallucinations plus delusions scores) and/or on the NPI agitation/aggression domain in patients treated with MP-101 compared to placebo at 10 weeks after the start of treatment. This assumes a true response rate of 65% in the MP-101 treatment group versus 35% in the placebo treatment group, using a one-sided Fisher's exact test with a 5% type 1 error rate. The operating characteristics of this analysis were studied through simulations, with non-informative priors for the parameters of the underlying assumed normal distribution of the scores.

10.2. Population Analysis

Population	Description
Evaluable	All patients in the Intent-to-Treat population who complete at least Visit 5
	(Week 4) with NPI efficacy data. Specifically, patients with a diagnosis of
	psychosis must have at least one psychosis sub-scale score at Visit 5 or later
	and patients with a diagnosis of agitation/aggression must have at least one
	agitation/aggression sub-scale score at Visit 5 or later.
	All patients in the Intent to Treat population who complete Visit 5 (Week 4)
	with NPI efficacy data.

10.3.3. Efficacy Analyses

10.3.3.1. Primary Analyses

The primary objective of this study will be assessed in the Evaluable population by analyzing the change from baseline to the 10-week treatment endpoint of the combined hallucinations and delusions scores from the NPI-Psychosis subscale NPI response rates. Response will be defined using two NPI endpoints: 1) the psychosis domain score, calculated as the sum of the delusions and hallucinations domain scores, and 2) the aggression/agitation domain score. Each domain score is the product of the severity and frequency ratings.

A patient with a 30% improvement from baseline on a subscale will be considered a responder for that subscale. At baseline, patients will be given a diagnosis of psychosis and/or agitation/aggression. A patient with a psychosis diagnosis will be considered an overall responder with a response on the psychosis subscale, a patient with a diagnosis of aggression/agitation will be considered an overall responder with a response on the aggression/agitation subscale, and a patient with both diagnoses will be considered an overall responder with a response on either subscale.

The primary analysis will use a one-sided Fisher's exact test with a 5% type 1 error rate.

The change from baseline to the 10-week time point (Visit 8 [Week 10]) will be estimated using repeated measures mixed models assuming data are missing at random, with covariates for baseline and the stratification factors. The Bayesian posterior probability that the mean change from baseline MP-101 score is better than the mean change from baseline placebo score by at

least 1 point will be calculated. Non-informative priors for the parameters of the normal distribution will be used

The precise analysis methods will be detailed in the SAP, which will be completed prior to database lock

10.3.3.2. Secondary Analyses

The secondary efficacy endpoints will be assessed by analyzing the change from baseline to the 10-week time point using analysis methods appropriate to the type of measurement. These Secondary efficacy outcomes include CGI-IS; NPI Total Score; NPI-Core Total (combination of 3 items: hallucinations, delusions, and agitation/aggression); NPI Caregiver Distress-D; NPI domain of anxiety, agitation/aggression, and sleep and nighttime behavior disorders; CMAI; MMSE; ADCS-ADL; and the UPDRS, Part III.

The delusions, hallucinations, and aggression/agitation domain scores will be added together to form a Core Total score. A patient with a 30% improvement from baseline will be considered a responder on the Core Total score. The treatment groups will be compared using a one-sided Fisher's exact test.

The psychosis and aggression/agitation domain scores, and the Core Total score, will be analyzed as continuous measures.

The change from baseline for quantitative endpoints will be analyzed using repeated measures mixed models assuming data are missing at random, with covariates for baseline and the stratification factors.

The CGI-I scores will be analyzed using Cochran-Mantel-Haenszel tests, stratifying by the randomization strata, and using modified Ridit scores (i.e. van Elteren tests).

10.3.3.3. Exploratory Analyses

The exploratory efficacy objectives to determine whether MP-101 is superior to placebo in patient behavior and caregiver burden. Changes in patient behavior will be assessed using ADCS-CGIC and NPI domains of depression/dysphoria, elation/euphoria, apathy/indifference, disinhibition, irritability/lability, aberrant motor behavior, sleep and nighttime behavior disorders, and appetite and eating disorders; MMSE. The analysis methods for the exploratory efficacy analyses will be detailed in the SAP.

The ZBI-22 is being utilized to assess caregiver burden.

The exposure-response relationships between efficacy and safety endpoints may also be explored, as needed, as detailed in the SAP.

Details of the analyses of exploratory efficacy outcomes will be detailed in the SAP.

10.3.6. Other Analyses

10.3.6.1. Pharmacogenetics Exploratory Analyses

To explore the effect of genotype on the response to MP-101 in AD-dementia patients with psychosis, genotype data for HTR2A SNP rs7330461, HTR2A SNP rs6313 (102T/C), APOE, and other genotypes may be analyzed. The analysis methods may be detailed in the SAP.

10.3.7. Interim Analysis

An interim analysis is planned for this trial which will occur after approximately 20 patients have completed Visit 5 (Week 4) to evaluate PK and safety. A second interim analysis may be performed to evaluate the futility of finding differences in the efficacy endpoints between treatment groups. All interim analysis details, including unblinding, plans and stopping rules for the futility analysis, will be documented in the Assessment Committee Charter.

Section 11. References

List of references was updated in line with the edits made in the main body text.

# **ABBREVIATIONS/DEFINITIONS**

Abbreviation	Definition
AE	Adverse Event
CRP	Clinical Research Physician
CSR	Clinical Study Report
C–SSRS	Columbia Classification Algorithm for Suicide Assessment
ECG	Electrocardiogram
eCRF	Electronic Case Report Form
Interim Analysis	An interim analysis is an analysis of clinical study data, separated into treatment groups, that is conducted before the final reporting database is created/locked
ITT	Intent-to-Treat
IWRS	Interactive Web-Response System
MedDRA	Medical Dictionary for Regulatory Activities
MMSE	Mini-Mental State Exam
NPI	Neuropsychiatric Inventory
РК	Pharmacokinetics
PT	Preferred Term
QD	Once daily (quaque die)
SAE	Serious Adverse Event
SAP	Statistical Analysis Plan
SOC	System Organ Class
TEAE	Treatment Emergent Adverse Event
TUG	Timed Up and Go
UPDRS Part III	Unified Parkinson's Disease Rating Scale, Part III
WHODD	World Health Organization Drug Dictionary
ZBI-22	Zarit Burden Interview - 22

# 1. INTRODUCTION AND OBJECTIVES

#### 1.1. Introduction

Study MP-101-01(b) is a Phase 2, multicenter, double-blind, 1:1 randomized, parallel, placebo-controlled, 10-week study of MP-101, consisting of screening, treatment, and follow-up periods, in patients with dementia-related psychosis and/or agitation and aggression.

This statistical analysis plan (SAP) describes the analysis variables and statistical procedures that will be used to analyze and report the results from Protocol MP-101-01(b), which was approved on 13 February 2017.

Some of the analyses detailed here may be more explicit or in some aspects different from those stated in the protocol. In case of differences, this SAP supersedes the statistical sections in the protocol.

Changes to the protocol that impact the design, the data collected, or the statistical methods and that occur after the finalization of this SAP may require amendment of the approved SAP. Similarly, changes to the planned analysis variables and/or statistical methods described in the approved SAP may also require amendment of the SAP.

The formats for the tables, listings, and figures described in this SAP are provided in a companion document. Changes to the formats of these reports that are decided after the finalization of the SAP will not require an amendment. In addition, any additional supportive or exploratory analyses requested after SAP approval will not require amendment of the SAP. These additional analyses will be described in the clinical study report (CSR).

See the study protocol for details about the study design, procedures, and schedule of assessments and see the electronic case report form (eCRF) for details about variables collected and their possible values.

The time and events schedule for this study is provided in Section 9.

EMB Statistical Solutions will have responsibility for performing these analyses.

## 1.2. Study Objectives and Endpoints

Table 1 shows the objectives and endpoints of the study.

#### Table 1. Objectives and Endpoints

Objectives	Endpoints
Primary	
To test the hypothesis that oral administration of once daily (QD) MP-101 will improve psychotic symptoms and/or agitation and aggression in patients with dementia when compared to	Change from baseline to 10-week treatment endpoint in the Neuropsychiatric Inventory (NPI)-Psychosis subscale (combination of 2 items: hallucinations and delusions) and/or in the agitation/aggression domain.

Objectives	Endpoints
placebo.	
Secondary	
To assess whether MP-101 is superior to placebo in the following: neuropsychiatric disturbances, caregiver distress, and anxiety.	Change from baseline to 10-week treatment endpoint in the following: Clinical Global Impression of Improvement (CGI-I); NPI Total Score; NPI-Core Total (combination of 3 items: hallucinations, delusions, and agitation/aggression); NPI Caregiver Distress; NPI domain of anxiety.
To determine if MP-101 is safe and tolerable.	Treatment-emergent adverse events (TEAES); Unified Parkinson's Disease Rating Scale (UPDRS) Part III.
To assess the PK of MP-101 and its primary active metabolite, LY2812223.	Plasma PK concentrations.
Exploratory	
To assess whether MP-101 is superior to placebo in changes in patient behavior and care- giver burden.	Change from baseline to 10-week treatment endpoint in the following: NPI domains of depression/dysphoria, elation/euphoria, apathy/indifference, disinhibition, irritability/lability, aberrant motor behavior, sleep and nighttime behavior disorders, and appetite and eating disorders; Mini- Mental State Examination (MMSE); Zarit Burden Interview-22 (ZBI-22).
To explore the effect of HTR2A and ApoE genotypes on response to treatment.	5-hydroxytryptamine serotonin 2A receptor (HTR2A) single nucleotide polymorphism (SNP) rs7330461 genotype data; HTR2A SNP rs6313 (102T/C) genotype data; ApoE genotype data.
To explore exposure-response relationships with efficacy and safety clinical endpoints, as needed.	Efficacy and safety clinical endpoints, as needed.

# **1.3.** Definition of NPI Response and Core Total Response

NPI response will be defined using two NPI endpoints: 1) the psychosis domain score, calculated as the sum of the delusions and hallucinations domain scores, and 2) the aggression/agitation domain score. Each domain score is the product of the severity and frequency ratings.

A patient with a 30% improvement from baseline on a subscale will be considered a responder for that subscale. At baseline, patients will be given a diagnosis of psychosis and/or agitation/aggression. A patient with a psychosis diagnosis will be considered an overall responder with a response on the psychosis subscale, a patient with a diagnosis of aggression/agitation will be considered an overall responder with a response on the aggression/agitation subscale, and a patient with both diagnoses will be considered an overall responder with a response on the aggression/agitation subscale, and a patient with both diagnoses will be considered an overall responder with a response on the aggression/agitation subscale.

The delusions, hallucinations, and aggression/agitation domain scores will be added together to form a Core Total score. A patient with a 30% improvement from baseline will be considered a responder on the Core Total score.

## **1.4.** Sample Size Determination

Approximately 100 patients will be enrolled to enable approximately 80 evaluable patients to complete the study through at least Visit 5 (Week 4).

The primary analysis will use a one-sided Fisher's exact test with a 5% type 1 error rate.

If the NPI response rate in MP-101 treated patients is 30% greater than in placebo treated patients (65% vs 35%), with 40 evaluable patients per treatment group there is at least an 80% chance (i.e. Power) that MP-101 will demonstrate superiority to placebo.

The sample size was calculated assuming an expected 20% drop-out rate of patients in each arm prior to Week 4, so that 100 patients are planned to be enrolled to arrive at 40 patients/arm (N=80) in the Evaluable population.

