The primary treatment effect will be measured as the difference in the percentage of patients with a response on either the NPI-Psychosis or Agitation/Aggression subscales at the end of the treatment period. A patient with a 30% improvement from baseline on a subscale will be considered a responder for that subscale. A patient with a psychosis diagnosis at screening will be considered an overall responder with a response on the NPI-Psychosis subscale, a patient with a diagnosis of agitation/aggression at screening will be considered an overall responder with a response on the NPI-Agitation/Aggression subscale, and a patient with both diagnoses will be considered an overall responder with a response on either subscale. The primary analysis will use a one-sided Fisher's exact test with a 5% type 1 error rate. The primary population for analysis will include all randomized patients who take at least 1 dose of double-blind study treatment and complete Visit 5 (Week 4) with NPI efficacy data (i.e., the Evaluable population).

The primary analyses will be performed with patients grouped by treatment arm (i.e., MP-101 or placebo) regardless of their final dose level.

2. Schedule of Activities

Schedule of Activities for Protocol MP-101-01

	Screen	Treatment Period (10 Weeks)			Follow- up					
Visit Number	V1	V2	V3a	V4	V5	V6	V7a	V8	V9	ET
Week	-1 to -5	0	1	2	4	6	8	10	11	
Days from Randomization (target)	-1 to-35	0	7	14	28	42	56	70	77	
Visit Window (± days from target)				2	2	2		2	2	
Study site visit	Х	Х		Х	Х	х		х	Х	Х
Informed Consent										
(before any procedures/tests)	X									
Clinical Assessments										
Demographics, height	X									
Weight	Х	Х		X	X	Х		Х	Х	X
Vital signs (BP and pulse)	Х	х		X	Х	Х		Х	Х	Х
Medical history and physical exam	Х									
Neurological exams	X	X						X		X
TUG (if applicable)	X	X		X	х	X		X	Х	
Concomitant medications	X	X	х	X	X	X	Х	X	X	X
Inclusion/exclusion review	X	xb	A		A			- 1	- 1	
Hepatitis B surface antigen,	Α	Α-								
Hepatitis C antibody, HIV	X									
Randomization		X								
Investigational product dispensing				v	v	v				
Dose administration at site		X		X	X	X				
Investigational product		X		X	X					
accountability				X	X	X		X		X
Symptom directed physical exam		v		v	v	v		v	v	v
Habits (alcohol, caffeine, nicotine,		X		X	X	X		X	X	X
tobacco)	X	X	X	X	X	X	X	X		X
Safety Measures										
Adverse event assessment	37	37		37		v		v	37	N/
	X	X	X	X	X	X	X	X	X	X
C-SSRS ^c	X	X		X	X	X		X	X	X
Single 12-lead ECG	X	X		X	X			X	X	X

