10.1. Sample Size Determination

Approximately 100 patients will be enrolled to enable approximately 80 evaluable patients to complete the study through at least Visit 5 (Week 4). The sample size was chosen so that there is at least an 80% chance the trial will show a statistically significant improvement in the response rate on the NPI-Psychosis scale (hallucinations plus delusions scores) and/or on the NPI-agitation/aggression domain in patients treated with MP-101 compared to placebo. This assumes a true response rate of 65% in the MP-101 treatment group versus 35% in the placebo treatment group, using a one-sided Fisher's exact test with a 5% type 1 error rate.

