10.3.3. Efficacy Analyses

10.3.3.1. Primary Analyses

The primary objective of this study will be assessed in the Evaluable population by analyzing NPI response rates. Response will be defined using two NPI endpoints: 1) the psychosis domain score, calculated as the sum of the delusions and hallucinations domain scores, and 2) the aggression/agitation domain score. Each domain score is the product of the severity and frequency ratings.

A patient with a 30% improvement from baseline on a subscale will be considered a responder for that subscale. At baseline, patients will be given a diagnosis of psychosis and/or agitation/aggression. A patient with a psychosis diagnosis will be considered an overall responder with a response on the psychosis subscale, a patient with a diagnosis of aggression/agitation will be considered an overall responder with a response on the aggression/agitation subscale, and a patient with both diagnoses will be considered an overall responder with a response on either subscale.

The primary analysis will use a one-sided Fisher's exact test with a 5% type 1 error rate.

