# 5. EFFICACY ANALYSES

## 5.1. Primary Analysis

The primary analysis of the NPI response rate will use a one-sided Fisher's exact test with a 5% type 1 error rate. The lower 95% confidence limit of the difference in NPI response rates (MP-101 minus Placebo) will be calculated using an exact unconditional confidence interval.

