## **Quantitative Endpoints**

The quantitative secondary efficacy endpoints will be assessed by analyzing the change from baseline to the 10-week time point in the Evaluable population using PROC MIXED to model the difference in the Week 10 change from baseline score between treatment groups and to handle missing assessments. The change from baseline to each scheduled post-baseline visit will be estimated using repeated measures mixed models assuming data are missing at random, with covariates for baseline and visit. The lower 95% confidence limit of the difference in mean scores at Week 10 (MP-101 minus Placebo) will be estimated from the mixed model. The effects of baseline domain scores and treatment will be allowed to vary across visits. The following SAS code will be used, for assessments at Weeks 2, 4, 6, and 10. For patients who withdraw prior to Week 10, NPI data from the early termination visit will be used as the next visit's assessment; for example, if a patient's last scheduled assessment is at Week 4, the early termination data will be included in the analysis as Week 6.

proc mixed;

class visit treatment patient; model psychosis=visit\*baseline visit\*treatment / s; repeated visit / type=vc subject=patient; random patient; estimate 'Trt Effect, week 10' visit\*treatment 0 0 0 0 0 0 1 -1/cl alpha=.10; run; In addition, plots of each least squares mean domain score ( $\pm$  standard error) for the psychosis, delusions, hallucinations, agitation/aggression, and total scores by scheduled visit will be created.

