#### **Ordinal Endpoints**

The Core Total Score response rate will be analyzed using a one-sided Fisher's Exact test. The lower 95% confidence limit of the difference in Core Total Score response rates (MP-101 minus Placebo) will be will be calculated using an exact unconditional confidence interval. The CGI-I will be analyzed using Cochran-Mantel-Haenszel tests using modified Ridit scores (i.e. van Elteren tests).

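### Efficiency improvement, not an error: Fisher's test uses about 3 of the 5 points of one-sided type I error allowed; Boschloo's exact test would add about 6 points of power at 40 per arm with no extra patients

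*SAP*

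**What the plan says.** The primary endpoint is NPI response in the Evaluable population, compared between arms by a one-sided Fisher's "exact test with a 5% type 1 error rate" (protocol 10.3.3.1). The protocol synopsis, protocol 10.1, SAP 1.4 and SAP 5.1 name the same test.

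On planning rates, protocol 10.1 states: "This assumes a true response rate of 65% in the MP-101 treatment group versus 35% in the placebo treatment group". SAP 1.4 adds that "with 40 evaluable patients per treatment group there is at least an 80% chance (i.e. Power) that MP-101 will demonstrate superiority to placebo". It enrols 100 patients to allow for "an expected 20% drop-out rate of patients in each arm prior to Week 4".

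SAP 5.1 accompanies the test with a lower 95% limit for the difference in response rates, which "will be calculated using an exact unconditional confidence interval". It does not name the statistic that orders the outcomes, and it does not say whether the 95% is one-sided. SAP 5.2 uses the same pairing for a secondary endpoint: "The Core Total Score response rate will be analyzed using a one-sided" Fisher test, again with an exact unconditional limit.

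**The concern.** Fisher's test conditions on the total number of responders. With 40 per arm its p-values are coarse, so the error rate it attains falls well below the declared 5%. The documents do not say that a lower rate was intended. The unused part could be spent on power with the same patients.

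There is also a reporting problem. A conditional p-value and an unconditional confidence limit come from different calculations and need not agree. If the limit is one-sided, the report could show a lower limit above zero beside a failed primary test.

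**Working it through.** **Inputs.** 40 evaluable per arm, 65% vs 35%, one-sided 5%, Fisher (SAP 1.4, protocol 10.1). 1:1 allocation (protocol 7.2). 100 enrolled with 20% drop-out (SAP 1.4): 80 / 0.8 = 100, or 50 per arm.

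**Formulas.** Let x and y be the responders on MP-101 and placebo, with n = 40 per arm.

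- Fisher: p_F(x, y) = Σ over k ≥ x of C(40, k)·C(40, x+y−k) / C(80, x+y). Reject if p_F ≤ 0.05.
- Power: the sum of Bin(x; 40, 0.65)·Bin(y; 40, 0.35) over rejected outcomes.
- Size: the maximum, over a common response rate π, of the rejection probability when both arms have rate π.
- Boschloo: p_B(x, y) = the maximum over π of Pr[p_F(X, Y) ≤ p_F(x, y)]. Reject if p_B ≤ 0.05.

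**The plan's figure.** Enumerating all 41 × 41 outcomes gives Fisher power of 79.5%, so the stated 80% is reproduced to within rounding. Fisher first passes 80% at 41 per arm (81.1%). The normal-approximation sample-size formula with continuity correction gives exactly 40 per arm.

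**The two tests at 40 per arm.**

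| | Fisher | Boschloo |
|---|---|---|
| Maximum size | 3.07% | 4.87% |
| Rejected outcomes | 568 | 599 (all 568, plus 31) |
| Power at 65% vs 35% | 79.5% | 85.4% |

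The gain is 85.4 − 79.5 = 5.9 points. Fisher reaches 85.3% at 44 per arm and 86.5% at 45, so the change is worth 4 to 5 evaluable patients per arm.

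**Other true rates at 40 per arm (Fisher to Boschloo).** 60% vs 30%: 79.8% to 85.6%. 55% vs 25%: 80.9% to 86.4%. 60% vs 35%: 63.9% to 72.1%.

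**Unequal splits.** Power at 65% vs 35%; which arm is larger does not matter, because the two rates are mirror images.

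| Split | Fisher | Boschloo |
|---|---|---|
| 38/38 | 76.6% | 82.6% |
| 38/42 | 80.1% | 85.4% |
| 39/40 | 81.9% | 83.6% |
| 39/41 | 79.7% | 85.5% |
| 40/41 | 83.3% | 83.9% |
| 41/42 | 84.7% | 85.1% |
| 42/42 | 82.6% | 86.9% |

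Over all 15 splits with 38 to 42 per arm, Fisher is below 80% in 5 and Boschloo in none. The gain runs from 0.4 to 6.2 points. Boschloo's maximum size runs from 4.69% to 5.00%.

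**Averaged over drop-out.** Assume the evaluable count in each arm is Binomial(50, 0.8), independently. Average power is 80.6% for Fisher and 84.9% for Boschloo. The realised split leaves power below 80% with probability 36% for Fisher and 1% for Boschloo. No split has an outcome that Fisher rejects and Boschloo does not.

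**Test against limit.** The mixed-model code in SAP 5.2 ends "0 0 0 0 0 0 1 -1/cl alpha=.10". That is a 90% two-sided interval, whose lower end is a one-sided 95% limit. Read SAP 5.1 the same way. At 24/40 vs 16/40 Fisher gives p = 0.0585 and fails. The unconditional p-value is 0.0465 and the lower limit is +0.4 points, whether outcomes are ordered by Fisher's p-value, by the score statistic or by the raw difference. Under 65% vs 35%, a failed Fisher test beside a limit above zero has probability 5.9%.

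**The case against.** Nothing in the plan is wrong. Fisher's test is valid, familiar and consistently named, and it delivers its stated power to within rounding. That is why this point is an improvement and not a correction.

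The gain also has a price: the maximum false-positive rate rises from 3.07% to 4.87%. At 40 per arm every added rejection is a borderline result, with Fisher p between 0.05 and 0.077. This is true, but the higher rate stays within the 5% that the sponsor declared.

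Exactly 40/40 is a favourable split. The gain is 0.6 points at 40/41 and 0.4 at 41/42, and 4.3 points on average over drop-out, under an assumption that the plan does not state. This stands as a limit on the size of the gain. Power is not lower in any split examined.

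The conflict between test and limit rests on reading the limit as one-sided, and the supporting code belongs to other endpoints. This stands too. If the limit is the lower end of a two-sided 95% interval ordered by Fisher's p-value, that conflict cannot occur at 40/40. The opposite one, Fisher rejecting while the limit is below zero, then has probability about 4.6% under 65% vs 35%. Changing only the test would not cure that, so the limit's level must be stated in either case.

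Finally, the SAP is final, patients are enrolled and unblinded interim looks are planned (SAP 3). A late switch to a test that can only add rejections would invite questions. The documents do not show whether a look has taken place, so timing is a real condition on the advice.

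**Conclusion.** The point holds as an efficiency improvement that should be made. At the plan's own scenario, Boschloo's test at the declared 5% cuts the chance of missing a true 65% vs 35% effect from 20.5% to 14.6%, with no added patients. Averaged over drop-out the gain is 4.3 points if losses are binomial and independent between arms. The gain persists at the other response rates examined. This is relevant because SAP 2.7 counts undeterminable responses as non-response, which could lower both rates. The power statement in SAP 1.4 is not a material error, although taken literally it is half a point high at 40 per arm. The mismatch between p-value and limit is a separate, smaller reporting matter whose form depends on the limit's level, which SAP 5.1 leaves open.

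**What to change.** Before any unblinded look at NPI response:

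- **Primary test.** Name Boschloo's test at one-sided 5% in SAP 5.1, protocol 10.3.3.1 and the protocol synopsis. Keep Fisher's test and the stratified Cochran-Mantel-Haenszel test as supporting analyses.
- **Confidence limit.** State that it is a one-sided 95% lower limit, obtained by inverting the same criterion: order outcomes by one-sided Fisher p-value and, for each difference, maximise the tail probability over the nuisance rate. At a difference of zero this is Boschloo's p-value, so test and limit agree.
- **Core Total response (SAP 5.2).** Do the same.
- **Power (SAP 1.4, protocol 10.1).** State about 85% for Boschloo. If Fisher is kept, state 79.5% at 40 per arm and still define the limit's level and ordering.

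A score test with a score-based limit is an acceptable alternative. It averages 84.3% power over drop-out and gives a tighter limit away from zero: at 26/40 vs 14/40 about +9.8 points, against +8.2 for the Boschloo-ordered limit. Its gain over Fisher is smaller at some unequal splits (0.04 points at 41/42). Raw-difference ordering is less suitable: it gains nothing at 42/42 and does not contain every Fisher rejection, although the outcomes it misses are very improbable under the planning rates at 40/40.

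**Cost.** No patients or visits. A SAP change is needed and probably a protocol amendment, since the primary test is plausibly a principal feature under protocol 10.3.1. The code needs the independent validation of SAP 2.1. Any futility rule in the Assessment Committee Charter must be checked against the new test. The test is less familiar to readers, and the attained type I error moves closer to 5%.
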